16.10. Appendix 10: Pharmacokinetic / Pharmacodynamic Analyses

16.10.1. Pharmacokinetic / Pharmacodynamic Dataset Specification

Dataset specifications for exposure-response analyses of efficacy and of corneal toxicity are provided. Any deviations between the dataset specifications and the final datasets will be documented in the population pharmacokinetic analysis report.

For corneal toxicity

Column Header	Data Item	Codes	Derivation/Comments	Source data set
C	Line number/exclusion identifier	Row Number	Set to line/row number	adae
STUDY	Study ID		1 = BMA117159	adsl
SUBJID	Subject identifier from source data		SUBJID = SUBJID	adsl
ID	NONMEM subject identifier		Sequential subject identifier across studies after data is sorted by SUBJID. Starting with PP	
TOXTYPE	This variable is created to separate out Grade 1 toxicity from Grade 2 and higher.	1,2	2 separate datasets with one line per subject: TOXTYPE = 1 for 1 st occurrence of corneal event (CQ01NAM = Corneal Event). If CQ01NAM = missing, add 1 line for that subject. TOXTYPE = 2 for 1 st occurrence of corneal event (CQ01NAM = Corneal Event) with AETOXGRN ≥ 2. If CQ01NAM = missing, add 1 line for that subject. After these 2 datasets are complete, merge them.	adae
CORTOX	Presence or Absence of Corneal toxicity	0 or 1	When CQ01NAM = "Corneal Event", then CORTOX=1. When CQ01NAM =missing, then CORTOX=0.	adae
AETOXGRN	Standard Toxicity Grade	0,1,2,3		adae
TTECORTOX	Time to corneal toxicity event (day)		
 For TOXTYPE = 1 and CORTOX = 1, then TTECORTOX = AESTDY When TOXTYPE = 1 and CORTOX = 0, then TTECORTOX = (TRTSDT, LSTCTDT is coming from adsl dataset) For TOXTYPE = 2 and CORTOX = 1, then 	adae, adsl

Column Header	Data Item	Codes	Derivation/Comments	Source data set
			TTECORTOX = AESTDY 
 When TOXTYPE = 2 and CORTOX=0, then TTECORTOX = LSTCTDT – TRTSDT+ 1 	
DOAE	Duration of adverse event (days)		
 When CQ01NAM = Corneal Event and AONGO=N and AENDT= blank, then DOAE = ADURN; When CQ01NAM = Corneal Event and AONGO = N and AENDT= D, then DOAE = -99; When CQ01NAM = Corneal Event and AONGO=Y, then DOAE = LSTCTDT – AESTDY + 1; When CQ01NAM = missing, then DOAE = 0; 	adae, adsl
DOAECFLCD	DOAE Censoring Flag Code	0 or 1	When AONGO=N, then DOAECFLCD=0 When AONGO=Y, then DOAECFLCD=1	adae
LNDOAE	Log of duration of adverse event		LNDOAE = Log(DOAE); When DOAE=-99, LNDOAE =-99; When DOAE=0, LNDOAE=0	adae

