TOTAUC	Total AUC (ug.day/mL)		(Total dose received)/Individual Clearance of ADC	popPK output
Q4TOTAUC	Quartile of TOTAUC	0,1,2,3		derived
Q5TOTAUC	Quintile of TOTAUC	0,1,2,3,4		derived
MMAFAUC	First dose AUC(0-inf) of MMAF (ug.day/mL)		First dose (mg)/Individual Clearance of MMAF	popPK output
Q4MMAFAUC	Quartile of MMAFAUC	0,1,2,3		derived
Q5MMAFAUC	Quintile of MMAFAUC	0,1,2,3,4		derived
MMAFTOTAUC	Total AUC (ug.day/mL)		(Total dose received)/Individual Clearance of MMAF	popPK output
Q4MMAFTOTAUC	Quartile of MMAFTOTAUC	0,1,2,3		derived
Q5MMAFTOTAUC	Quintile of MMAFTOTAUC	0,1,2,3,4		derived

For efficacy

Column Header	Data Item	Codes	Derivation/Comments	Source data set
C	Exclusion identifier	Row Number DORDM	Set to line/row number unless one or more of the following conditions are met, then set to code: 
 DORDM: If DORD is missing 	adtte
STUDY	Study ID		1 = BMA117159	adsl
SUBJID	Subject identifier from source data		SUBJID = SUBJID	adsl
ID	NONMEM subject identifier		Sequential subject identifier across studies after data is sorted by SUBJID. Starting with P	derived
PFSCFLCD	PFS Censoring Flag Code	0 or 1	For PARAMCD=PFS_D, CNSR value is assigned to PFSCFLCD 0=Event 1=Censor	adtte
PFSD	PFS (Days)		For PARAMCD=PFS_D, AVAL value is assigned to PFSD	adtte
PFSM	PFS (Months)		For PARAMCD=PFS_M, AVAL value is assigned to PFSM	adtte
PFSY	PFS (Years)		For PARAMCD=PFS_D, (AVAL/365) value is assigned to PFSY	derived
TTRCFLCD	TTR Censoring Flag Code	0 or 1	For PARAMCD=TTR_D, Assign 1 to TTRCFLCD. For subjects where TTR_D is missing, assign 0 to TTRCFLCD.	adtte
TTRD	TTR (Days)		For PARAMCD=TTR_D, AVAL value is assigned to TTRD. For subjects where TTR_D is missing, assign PFSD to TTRD.	adtte
TTRM	TTR (Months)		For PARAMCD=TTR_M, AVAL value is assigned to TTRM. For subjects where TTR_M is missing, assign PFSM to TTRM.	adtte
TTRY	TTR (Years)		For PARAMCD=TTR_D, (AVAL/365) value is assigned to TTRY. For subjects where TTR_D is missing, assign PFSY to TTRY.	derived
DORCFLCD	DOR Censoring Flag Code	0 or 1	For PARAMCD=DOR_D, CNSR value is assigned to DORCFLCD 0=Event 1=Censor Assign "." for missing.	adtte
DORD	DOR (Days)		For PARAMCD=DOR_D, AVAL value is assigned to DORD. For subjects where DOR_D is missing, assign "."	adtte

Column Header	Data Item	Codes	Derivation/Comments	Source data set
DORM	DOR (Months)		For PARAMCD=DOR_M, AVAL value is assigned to DORM. For subjects where DOR_M is missing, assign “.”	adtte

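### As written, the Grade 2+ corneal dataset has no correct place for Grade 1-only subjects, and the time-to-response flag is coded against its own label as a censoring flag

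*SAP*

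**What the plan says.** All the derivations are in SAP 16.10.1.

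**Corneal toxicity table**
- TOXTYPE calls for "2 separate datasets with one line per subject". The second dataset takes the first "occurrence of corneal event (CQ01NAM = Corneal Event) with AETOXGRN ≥ 2. If CQ01NAM = missing, add 1 line for that subject". The add-a-line sentence is the same one used for TOXTYPE=1, and the cell ends: "If CQ01NAM = missing, add 1 line for that subject. After these 2 datasets are complete, merge them".
- CORTOX is defined once for both datasets: "When CQ01NAM = 'Corneal Event', then CORTOX=1. When CQ01NAM =missing, then CORTOX=0". It has no condition on grade or TOXTYPE.
- TTECORTOX is the onset day (AESTDY) when CORTOX=1. For TOXTYPE=2 with CORTOX=0 it is LSTCTDT – TRTSDT + 1.
- Duration of an ongoing event begins "When CQ01NAM = Corneal Event and AONGO=Y, then DOAE = LSTCTDT" and then subtracts AESTDY and adds 1. Its censoring flag, DOAECFLCD, is 1 when the event is ongoing.

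**Efficacy table**
- For PFS: "CNSR value is assigned to PFSCFLCD 0=Event 1=Censor". The DOR flag has the same legend.
- TTRCFLCD is also named a censoring flag but has no legend. It is 1 where a time to response exists. Otherwise: "For subjects where TTR_D is missing, assign 0 to TTRCFLCD", with PFS time substituted as the time.

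**Analyses that use these variables.** SAP 16.10.2.2.1 plans logistic regression at two thresholds (Grade 1 or higher, Grade 2 or higher) and Kaplan-Meier plots of time to first corneal toxicity. SAP 16.10.2.2.2 plans Kaplan-Meier plots of time to response by exposure quartile and quintile.

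**The concern.** At the Grade 1 threshold, having no corneal event and being a non-event are the same thing, so adding a line when CQ01NAM is missing works. At the Grade 2 threshold, the non-events also include subjects whose only corneal events were Grade 1. The sentence was carried over without allowing for them, and no written rule codes them as 0.

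At stake is the Grade 2+ exposure-response analysis of corneal events, which SAP 8.2 lists among the adverse events of interest. The time-to-response flag is a second risk. Four flags in the specification share the censoring label and three run one way. An analyst who applies the label, or the common convention, to the fourth would count non-responders as responses. All the flags are 0/1, so nothing in the data would signal the mistake.

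**Working it through.** The SAP states no counts or rates for these analyses, so there is no plan figure to reproduce. The check applies the rules literally to each type of subject and then shows the size of the error under stated assumptions.

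**1. TOXTYPE=2, rule by rule**

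| Corneal events | CQ01NAM | Event of grade ≥ 2? | TOXTYPE=2 line | CORTOX | Should be |
|---|---|---|---|---|---|
| None | missing | no | added | 0 | 0 |
| Grade 2+ only | Corneal Event | yes | selected | 1 | 1 |
| Grade 1, then Grade 2+ | Corneal Event | yes | selected | 1 | 1 |
| Grade 1 only | Corneal Event | no | none | 1 if a line is forced | 0 |

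Only the last row fails. If a line is forced to honour the one-line rule, TTECORTOX would take the Grade 1 onset day as the time of a Grade 2+ event.

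**2. Direction and size.** Let p1 be the share with Grade 1 only and p2 the share with Grade 2+.
- Correct proportion: p2.
- Grade 1-only subjects omitted: p2 / (1 – p1), which exceeds p2 whenever p1 and p2 are above 0.
- Grade 1-only subjects coded 1: p2 + p1, which exceeds p2 whenever p1 is above 0.

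The direction needs no further assumption. The size does.

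| Assumed none / Grade 1 only / Grade 2+ | Correct | Omitted | Coded 1 |
|---|---|---|---|
| 35 / 20 / 45% | 45% | 45/80 = 56% | 45 + 20 = 65% |
| 30 / 30 / 40% | 40% | 40/70 = 57% | 40 + 30 = 70% |

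A wider range uses 40 subjects, the maximum size of the myeloma expansion cohort in SAP 3.1.2.1.1, with 4, 8 or 12 assumed Grade 1-only subjects:

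| Assumed Grade 2+ | Correct | Omitted | Coded 1 |
|---|---|---|---|
| 8 | 20% | 22–29% | 30–50% |
| 14 | 35% | 39–50% | 45–65% |
| 20 | 50% | 56–71% | 60–80% |

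At the low end the effect is small: 8/36 = 22% against 8/40 = 20%.

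**3. Flags side by side**

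| Flag | Event | Censored | Legend given |
|---|---|---|---|
| PFSCFLCD | 0 | 1 | yes |
| DORCFLCD | 0 | 1 | yes |
| DOAECFLCD | 0 (not ongoing) | 1 (ongoing) | stated in the rule |
| TTRCFLCD | 1 (response) | 0 (no response) | no |

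SAP 7.3.1.2.4 limits time to response to confirmed responders, so a missing value means no response. If TTRCFLCD were read with the PFS/DOR legend in a cohort of 40, then 8, 16 or 24 responders (assumed) would be analysed as 32, 24 or 16 responses. All of these would be non-responders timed at their PFS time.

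**4. Duration of ongoing events.** The same table uses AESTDY as a number of days (TTECORTOX = AESTDY) and LSTCTDT as a calendar date (LSTCTDT – TRTSDT + 1). LSTCTDT – AESTDY + 1 therefore subtracts a day count from a date and is not a duration.

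**The case against.** **The TOXTYPE=2 rule can be read benignly.** If CQ01NAM is tested for missing after the Grade 2+ filter has been applied and the result merged with all subjects, Grade 1-only subjects would receive CORTOX=0. The table already provides a censoring time for TOXTYPE=2 with CORTOX=0. This reading is possible but not written. CQ01NAM is a source variable in the adverse-event dataset, and it is populated for these subjects.

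**The response flag is coherent in itself.** Its row states both values outright, and 1 for response with PFS time for the rest is a valid event indicator. A reader might infer that responders are analysed as censored and every event status inverted. The document does not say so. Inversion occurs only if the label or another row's legend overrides the stated derivation. What stands is a contradictory label and a missing legend.

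**The duration formula has little consequence.** It would give visibly absurd values, and no analysis in SAP 16.10.2.2.1 uses duration. It is a minor correction.

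**Safeguards and scope.** The SAP says that deviations between the specification and the final datasets will be documented. That does not help here, because a programmer who follows the text exactly has no deviation to report. The scope argument does stand: exposure relationships with safety and activity are exploratory objectives (SAP 2.2), and these analyses are reported separately (SAP 12.1 and 16.10.2).

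**Conclusion.** The specification needs correcting, as a should-fix before the datasets are built. Followed literally, it omits Grade 1-only subjects from the Grade 2+ dataset. If a line is forced, it codes them as events. Both outcomes overstate the Grade 2+ proportion in the logistic analysis, and in any time-to-event analysis using the TOXTYPE=2 lines, whenever Grade 1-only subjects exist. The direction follows from the rules. The sizes, such as 45% becoming 56% or 65%, rest on assumed shares. The time-to-response flag is a labelling inconsistency that could invert the plots, not evidence that it has.

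Three stronger readings are not supported:
- **That the exposure slope is overstated.** No slope was computed. With omission it would be exaggerated if Grade 1-only subjects had intermediate exposure, which is plausible but not shown. If they are coded 1, the analysis becomes the Grade 1+ analysis. Under proportional odds the two thresholds share one slope, so no overstatement follows.
- **That the evidence on dose is compromised.** Part 1 dose decisions rest on the N-CRM estimates and the totality of the data (SAP 3.1.1), and the expansion dose is already set in SAP 5.1.
- **That the severity model uses the wrong grade.** The derivation cell for AETOXGRN is blank, so first-occurrence grade is only an inference from the row structure.

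The main ORR, PFS, DOR and safety tables do not use these variables and are unaffected.

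**What to change.** In SAP 16.10.1:
1. **TOXTYPE=2 and CORTOX.** Include one line for every subject in the exposure-response analysis set. Set CORTOX=1 only if the subject has a corneal event of grade ≥ 2. Otherwise set CORTOX=0 with TTECORTOX = LSTCTDT – TRTSDT + 1, and state that this covers Grade 1-only subjects.
2. **TTRCFLCD.** Code 0 for response and 1 for censored, matching the other flags. Alternatively, keep the values, rename it an event flag and add a legend.
3. **DOAE for ongoing events (minor).** Compute it from two dates: LSTCTDT minus the adverse-event start date, plus 1.

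The cost is a few lines in the specification and no new data. If the datasets already exist, check how Grade 1-only subjects and the response flag were handled, and re-derive where needed.

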7.3.1.2.6. Overall Survival

Overall survival (OS) is defined as the time from the date of first dose until death from any cause. For subjects who do not die, time of death will be censored at the date of last contact.

The protocol is amended to collect long-term survival data (i.e. up to 1 year after last subject completes or discontinues treatment). Subjects who are already completed the study will be contacted to request re-consent.

If all the patients (who were alive at the time of study completion) can be re-consented, OS landmark analysis may be performed at 9 and 12 months using Kaplan-Meier analysis as data permits. A listing of OS will also be provided. The OS landmark analysis will be based on Part 2 MM population; listing of OS will be based on All Treated MM population.

Otherwise, only descriptive analysis (number and % of deaths and lost to follow-up) will be performed.

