16. Sample(s) collected for analysis at central lab. The same sample will be used for BCMA (flow) and PD. On D8 only postdose PD assessment will be performed, if applicable (refer to footnote 18).
17. FISH testing at least for: t(4;14), t(14;16), 17p13del. FISH results from samples taken within 60 days prior to first dose are acceptable.
18. **Additional samples may be collected in some subjects (up to 6) for further exploration of PD.**
19. Archival tissue from up to 60 days prior to study is acceptable.
20. Collect sBCMA at C1D1 predose (within 30 minutes prior to SOI) and at EOI (± 5 minutes), C2D1 at predose (within 30 minutes prior to SOI) and at EOI (± 5 minutes).
21. Collect cytokines at predose (within 30 minutes prior to SOI) and EOI (± 5 min) (even when infusion is interrupted or halted) to assess allergic reaction
22. All ADA samples will be collected prior to each infusion
23. Flow cytometry performed central laboratory.
24. PK samples to be taken for both GSK2587916 and cys-mcMMAF measurement on C1D1, C2D1, C3D1, and C5D1 at predose (within 30 minutes prior to SOI) and at EOI (just before EOI).
25. Collect 1 PK sample at each subject's final visit.
26. Informed consent for optional genetics research should be obtained before collecting a sample.
27. Study drug administration ± 3 day window only.
28. Prophylaxis with prednisolone phosphate 1% or dexamethasone 0.1% 1 drop QID x 4 days starting 1 day prior to treatment
29. All participants should be followed for survival for 1 year from last subject last dose. and whether subsequent treatment for disease was given. Subject does not need to come in for visit. Participants who have completed treatment or the 3 month follow up visit (end of study) prior to amendment 5 will be reconsented for further follow up and survival status.
30. e-Diary to be completed at screening, then Days 1-7, 8, 15 of each treatment cycle. Upon implementation of the e-Diary, these assessments will be required.
31. OSDI and NEI-VFQ-25 to be administered during end of study treatment visit. Additional assessments for subjects who are experiencing corneal symptoms to be completed via telephone on a monthly basis for up to 1 year, or until resolution of symptoms (whichever comes first) during the follow-up period.
32. Exit interview to be performed within 21 days of end of study visit

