33. Optional follow-up telephone interview to explore visual symptoms and changes in symptoms and related impacts following treatment discontinuation be performed at least 6 months following the End of Study Treatment visit. This interview would only be for those subjects who experienced corneal symptoms during treatment and consent to participate.
34. End of treatment visit should be performed within 30 days (+7 days) after the last dose or prior to the start of new anti-cancer treatment, whichever is earlier. In cases where more than 30 days (+7 days) have elapsed from the date of the subject's last dose due to dosing delays and a subsequent decision to take the subject off treatment, the end of study treatment visit should be scheduled as soon as possible to allow the final assessments to be performed at the earliest date.

35. Participants with corneal signs or symptoms at the end of study treatment visit should be monitored by ophthalmic exam once a month after the last study dose until deemed clinically stable by an eye care professional complete resolution or for 12 months (whichever comes first). Corneal exams to include BCVA and slit lamp examination (with special focus on cornea). Participants who have completed treatment or the 3 month follow up visit (end of study) will be re-consented for additional ophthalmology follow up.

Abbreviations:

ADA = Antibody Drug Antibody; ALP = alkaline phosphatase; BCVA = best corrected visual acuity; BNP = B-type natriuretic peptide; C1D1 = Cycle 1 Day 1, etc.; cfdNA = Circulating free DNA; CK = creatinine kinase; CRP = C-reactive protein; EM = extramedullary; EOI = End of Infusion; FLC = free light chain; PD = Pharmacodynamics; PK = Pharmacokinetics; QID = 4 times a day; SOI = start of infusion; SPEP = serum protein electrophoresis; UPEP = urine protein electrophoresis

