16.10.2.2. Exposure-Response Analyses**16.10.2.2.1. Corneal Toxicity**

Presence or absence of corneal toxicity will be described using a conventional logistic regression model for both \geq Grade 1 and \geq Grade 2 toxicity. Time to first corneal toxicity will be explored using Kaplan Meier plots with exposure subdivided into quartiles and quintiles. Severity of corneal toxicity will be analyzed using an ordered logistic regression model assuming Grades 0 (no toxicity), 1, 2 and 3, with exposure subdivided into quartiles and quintiles.

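### Corneal exposure-response dataset: event-free subjects are censored at an undefined last-contact date, beyond the last scheduled eye exam, which can lower the Kaplan-Meier corneal risk and dilutes time-average AUC

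*SAP*

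**What the plan says.** **Censoring rule (SAP 16.10.1, corneal toxicity).** For Grade 2 or higher: "When TOXTYPE = 2 and CORTOX=0, then TTECORTOX = LSTCTDT – TRTSDT+ 1". For any grade, the formula breaks off: "TTECORTOX = (TRTSDT, LSTCTDT is coming from adsl dataset". The same two dates are named, so the same rule is presumably meant. LSTCTDT is not defined. In Section 7.3.1.2.6 the last contact is the survival censoring date: "For subjects who do not die, time of death will be censored at the date of last contact". Section 16.7.2.1 also places a last contact date in the overall survival dataset.

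**Ocular follow-up.** In Part 2 MM (16.2.3.1, footnote 35), "Participants with corneal signs or symptoms at the end of study treatment visit should be monitored by ophthalmic exam once a month". The lymphoma schedule (16.2.3.3, footnote 27) has the same restriction. The Part 1 schedule (16.2.2.1) lists no ocular exam at the 3-month contact.

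**Survival follow-up.** In Part 2 MM (16.2.3.1, footnote 29), "All participants should be followed for survival for 1 year from last subject last dose", and no visit is required.

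**Use (16.10.2.2.1).** "Time to first corneal toxicity will be explored using Kaplan Meier plots with exposure subdivided into quartiles and quintiles". TTECORTOX is also the end point of the time-average AUC variable TAAUCCT.

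**Duration of ongoing events (16.10.1).** "then DOAE = LSTCTDT – AESTDY + 1".

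**The concern.** A subject free of corneal signs at end of treatment has no further scheduled eye exam but may remain in the risk set as event-free for many months. Subjects with signs are examined monthly. The extra event-free time is longest, relative to time observed, for subjects who stop treatment early. If exposure groups differ in time on treatment, the planned comparison of curves across quartiles and quintiles is then affected unequally.

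The same date enters the exposure metric. TAAUCCT divides exposure by time to TTECORTOX. Subjects with an event are averaged up to their event, while event-free subjects are averaged over treatment plus off-drug follow-up. That moves event-free subjects towards low exposure for a reason unrelated to how they were dosed.

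The SAP takes the opposite approach for PFS: it censors at the last adequate assessment (7.3.1.2.1), and after a gap of more than 49 days it discards even an observed progression or death (16.5.4). No reason is given for treating corneal toxicity differently.

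**Working it through.** The SAP states no figure for time to corneal toxicity, so there is none to reproduce.

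**1. Direction of the Kaplan-Meier effect.** Estimated risk is 1 − Π(1 − dᵢ/nᵢ). Moving the censoring date of non-events later leaves every dᵢ unchanged and can only raise nᵢ. With the same events, risk under last-contact censoring is never above risk under last-exam censoring.

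**2. Size, under assumptions.** Simulations with n = 35, exponential event times, a hazard that continues after treatment, and no event recorded after the last exam:

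- True 180-day risk 60%, last exam 30 days after last dose, last contact 365 days after that exam. With median treatment of 42, 90 and 180 days, last-contact censoring gave 33%, 43–44% and 50%. Last-exam censoring gave 58–60%.
- A wider grid: median event time 30 to 300 days, median treatment 60 to 240 days beyond day 30, last contact 60 or 335 days after end of treatment. The shortfall was about 0.01–0.09 at day 90, 0.02–0.23 at day 180 and 0.02–0.34 at day 365.
- One case from that grid (event median 150 days, treatment median 120, gap 335):

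| Day | True | Censored at end of treatment | Censored at last contact |
|---|---|---|---|
| 90 | 0.340 | 0.346 | 0.313 |
| 180 | 0.565 | 0.563 | 0.433 |
| 365 | 0.815 | 0.798 | 0.504 |

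**3. When the lower curve is correct.** Take the 42-day case: λ = −ln(0.4)/180 = 0.00509 for events and μ = ln 2/42 = 0.01650 for stopping treatment. The probability of an event by day 180 and before the last exam is

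1 − e^(−30λ) + e^(−30λ) · λ/(λ+μ) · (1 − e^(−150(λ+μ))) = 0.142 + 0.858 × 0.236 × 0.961 = 0.336.

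This matches the simulated 33%. If no corneal event can start after treatment stops, 0.336 is the true cumulative incidence and 58–60% is too high.

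**4. Time-average AUC.** For an event-free subject no dose follows the last one, so cumulative AUC is the same under either end date and only the denominator changes. With 21-day cycles, last dose is on day 21 × (cycles − 1) + 1. End of treatment is taken as 30 days later (16.2.3.1, footnote 34). The factor is end-of-treatment day ÷ last-contact day; the contact times are assumptions.

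| Cycles | Last dose | End of treatment | Contact at +365 days | Contact at +92 days |
|---|---|---|---|---|
| 2 | 22 | 52 | 52/387 = 0.13 | 52/114 = 0.46 |
| 4 | 64 | 94 | 94/429 = 0.22 | 94/156 = 0.60 |
| 8 | 148 | 178 | 178/513 = 0.35 | 178/240 = 0.74 |
| 16 | 316 | 346 | 346/681 = 0.51 | 346/408 = 0.85 |

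The dilution arises whether or not corneal risk continues off treatment.

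**5. Duration of ongoing events.** AESTDY is a study day: the TTECORTOX row uses it directly as a time in days. LSTCTDT is a date. For a last contact of 1 January 2018 (SAS date 21185) and onset on day 40, both illustrative, the formula gives 21185 − 40 + 1 = 21,146 days. The log-duration variable inherits the value.

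**The case against.** A reader might infer that corneal risk is understated outright. The SAP does not support that, for five reasons.

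- **The event is a reported adverse event, not an exam finding.** CORTOX is set from the AE dataset, and Section 8.7 keeps exam signs apart from reported corneal events. The schedules show AE collection as continuous with no stated end, and the treatment-emergent definition (16.4.2) has no upper limit. A symptomatic late event could still be recorded. What certainly stops is scheduled examination.
- **Understatement needs risk or undetected events after treatment.** Step 3 of the working shows that the same data can make the lower curve correct. The SAP does not say which case applies.
- **Net direction in the Grade 2 or higher dataset is open.** A non-event line is added only where no corneal event of any grade exists, so Grade 1-only subjects appear to get no line. That pushes risk upward.
- **The gap varies.** LSTCTDT as survival contact is an inference. Follow-up to one year after the last subject's last dose belongs to the Part 2 MM schedule; Part 1 has a 3-month contact, with longer follow-up subject to re-consent. The 33% versus 50% contrast compares treatment durations, not the planned exposure groups.
- **Reach is limited.** The time variable feeds exploratory plots reported separately. The AE summaries of Section 8.2 do not use it, and the logistic and ordered models use presence or grade as outcome. No analysis in 16.10.2.2.1 uses the duration variable, and a value near 21,000 days would be noticed.

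All of this stands as a limit on the claim. It does not remove the mismatch between the censoring date and scheduled ascertainment, the diluted exposure metric, or the two formula errors. It also bears on the remedy: moving only non-events back to the last exam, while late-reported AEs still count, would bias risk upward.

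**Conclusion.** The point holds in limited form. Event-free subjects accrue time without scheduled eye exams under an undefined date. Relative to censoring at the last exam, this can only lower or leave unchanged the Kaplan-Meier corneal risk. Whether that is understatement depends on risk or undetected events persisting off treatment. Under that assumption the simulated shortfall at day 180 ranged from 0.02 to 0.23; no size can be derived from the SAP.

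The dilution of time-average AUC does not need that assumption. It depends on how long after last dose the last contact falls: a factor of 0.13 to 0.51 at 365 days and 0.46 to 0.85 at 92 days, for 2 to 16 cycles. It can exaggerate the exposure-response wherever that metric is the grouping variable or predictor, even though the 0/1 outcomes themselves are untouched.

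The duration formula is wrong as written and the TOXTYPE = 1 formula is incomplete; both are plain corrections. The consequences are confined to exploratory analyses, but the change is cheap and worth making.

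**What to change.** In SAP 16.10.1:

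1. Define LSTCTDT.
2. For both TOXTYPE levels, censor CORTOX = 0 at the end of corneal ascertainment. Use either the later of the last ocular exam and the end-of-treatment visit, or the documented end of corneal AE collection, and state which.
3. Apply the same cut-off to events: do not count an event starting after it unless the matching at-risk time is also kept.
4. Compute time-average AUC to that same date.
5. Complete the TOXTYPE = 1 formula.
6. For ongoing events, set DOAE = last ocular exam date − AE start date + 1, and keep the censoring flag.
7. Keep last-contact censoring as a sensitivity plot.

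The cost is a few lines of specification; ocular exam dates are already collected. The downside is fewer subjects at risk at late times and wider late confidence bands.

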16.6. Appendix 6: Derived and Transformed Data

16.6.1. General

Multiple Measurements at One Analysis Time Point

 • Mean of the measurements will be calculated and used in any derivation of summary statistics but if listed, all data will be presented. • Participants having both High and Low values for Normal Ranges at any post-baseline visit for safety parameters will be counted in both the High and Low categories of Any visit post-baseline row of related summary tables. This will also be applicable to relevant Potential Clinical Importance summary tables.
Study Day

 • Calculated as the number of days from First Dose Date: 
 • Ref Date = Missing → Study Day = Missing • Ref Date < First Dose Date → Study Day = Ref Date - First Dose Date • Ref Date ≥ First Dose Date → Study Day = Ref Date - (First Dose Date) + 1

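### The duration rule for ongoing corneal events subtracts a study-day number from a calendar date

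*SAP*

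**What the plan says.** SAP 16.10.1 specifies the dataset for the exposure-response analysis of corneal toxicity. It includes the duration of the event in days (DOAE), its logarithm (LNDOAE) and a censoring flag (DOAECFLCD), which is 1 when the event is ongoing (AONGO=Y) and 0 when it is not.

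- Ongoing events: "When CQ01NAM = Corneal Event and AONGO=Y, then DOAE = LSTCTDT – AESTDY + 1".
- Resolved events, first rule: "When CQ01NAM = Corneal Event and AONGO=N and AENDT= blank, then DOAE = ADURN".
- Resolved events, second rule: "When CQ01NAM = Corneal Event and AONGO = N and AENDT= D, then DOAE = -99".
- Log duration: "LNDOAE = Log(DOAE); When DOAE=-99, LNDOAE =-99; When DOAE=0, LNDOAE=0".

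The same table shows what kind of variable each term is. The time-to-event rule for subjects without an event is "When TOXTYPE = 2 and CORTOX=0, then TTECORTOX = LSTCTDT – TRTSDT+ 1", and for subjects with an event it is "For TOXTYPE = 1 and CORTOX = 1, then TTECORTOX = AESTDY". SAP 16.6.1 defines study day from first dose: "Ref Date ≥ First Dose Date → Study Day = Ref Date - (First Dose Date) + 1".

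**The concern.** LSTCTDT is differenced with the treatment start date to give days, so it is a date. AESTDY is assigned directly as a time in days, so it is a study-day number. Subtracting the second from the first mixes two scales, and the onset date needed for a duration never enters the rule.

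The affected records are all the ongoing events, which are all the censored durations in the dataset. Unresolved corneal findings matter in this study: SAP Section 1 records that the last listed protocol amendment added ocular follow-up for subjects whose corneal signs or symptoms had not resolved. If DOAE, LNDOAE and DOAECFLCD were used together to describe how long corneal toxicity lasts, the censored part of the data would be unusable.

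The rules for resolved events have a smaller fault. They test AENDT, the end date, for the values blank and D, and D is not a date.

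**Working it through.** **Ongoing events: the size of the error.** The SAP gives no worked figure to reproduce, so the check is algebra followed by examples.

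For an onset on or after first dose, the study-day definition in SAP 16.6.1 gives

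AESTDY = AESTDT − TRTSDT + 1, so AESTDT = TRTSDT + AESTDY − 1,

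where AESTDT is the start date of the event (the table does not list this variable).

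- Intended duration: LSTCTDT − AESTDT + 1 = (LSTCTDT − TRTSDT + 1) − AESTDY + 1.
- Duration as written: LSTCTDT − AESTDY + 1.
- Written minus intended: AESTDT − AESTDY = TRTSDT − 1.

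The error is therefore the numeric value of the treatment start date, less one. It depends on when the subject was first dosed and not on the event.

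**Examples.** Two inputs are assumptions. Dates are taken as SAS day counts from 1 January 1960. First doses are taken to lie between the first and last protocol versions listed in SAP Section 1 (26 December 2013 and 2 November 2017), with the version of 5 May 2016 as a middle value. TRTSDT − 1 is then 19,717, 20,578 and 21,124. The onset and last-contact days are illustrative.

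| Onset day | Last contact day | True DOAE (ln) | As written, first dose 26 Dec 2013 (ln) | As written, 5 May 2016 (ln) | As written, 2 Nov 2017 (ln) |
|---|---|---|---|---|---|
| 22 | 100 | 79 (4.37) | 19,796 (9.89) | 20,657 (9.94) | 21,203 (9.96) |
| 43 | 200 | 158 (5.06) | 19,875 (9.90) | 20,736 (9.94) | 21,282 (9.97) |
| 64 | 365 | 302 (5.71) | 20,019 (9.90) | 20,880 (9.95) | 21,426 (9.97) |

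For the second row, the true value is 200 − 43 + 1 = 158 and the written value with the earliest first dose is 158 + 19,717 = 19,875.

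On the log scale the true values span 5.71 − 4.37 = 1.34. All nine written values span 9.97 − 9.89 = 0.08, and what spread remains comes mostly from calendar date. Moving first dose from the earliest to the latest date shifts DOAE by 21,124 − 19,717 = 1,407 days. The true durations differ by at most 302 − 79 = 223 days.

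**Resolved events: the rules beside the missing-date conventions.** SAP 16.7.2.1 lets AE end dates lack the day, bars imputed partial dates from the derivation of durations, and leaves duration missing when a date is wholly absent.

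- If AENDT is read as the date, the first rule gives a duration to an event with no end date. That conflicts with 16.7.2.1, and a recorded end date matches neither rule.
- If AENDT is read as an end-date imputation flag, blank means a complete date and ADURN is right. D means an imputed day, and −99 agrees with 16.7.2.1.

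Only the second reading gives D a meaning, so the likely fault is a wrong variable name. On that reading the table still has no stated rule for a resolved event whose end date is wholly missing.

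**The case against.** The strongest objection is that no planned result is shown to be damaged. SAP 16.10.2.2.1 specifies logistic regression for presence of corneal toxicity, Kaplan-Meier plots for time to first event and ordered logistic regression for grade. None of these uses duration. The onset and duration summaries in SAP 8.2 (Tables 3.0180 to 3.0183) are separate displays and are not said to draw on DOAE. Durations of more than 50 years would also be noticed, and 16.10.1 requires differences between the specification and the final dataset to be documented. All of this stands, and it makes the point minor. It does not make the rule correct.

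Three stronger readings are tempting, and the SAP supports none of them.

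- A reader might infer that durations are wrong for most corneal events. The SAP gives no split between ongoing and resolved events. With the blank and D values read as an imputation flag, only the ongoing share is wrong. If that share were anywhere from 10% to 70% (an assumption), so would be the share of wrong durations.
- A reader might infer that resolved events with a recorded end date get no duration. That follows only if AENDT is read literally, and then D has no meaning.
- A reader might infer from "When DOAE=0, LNDOAE=0" that event-free subjects are confused with one-day events, since ln(1) is also 0. The same record carries CORTOX (0 or 1) and DOAE (0 or 1 day), so the two can be told apart.

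**Conclusion.** The rule for ongoing corneal events is wrong as written, and no reading of it gives a duration. It overstates DOAE by TRTSDT − 1 for every ongoing event, provided that onset is on or after first dose. The figures of 19,717 to 21,124 days and a LNDOAE of about 9.9 to 10.0 rest on SAS date storage and on the assumed range of first-dose dates. The mismatch of scales rests on neither. In the rules for resolved events the defect is a misnamed variable and an unstated rule for a missing end date.

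The severity is minor. The harm is confined to this dataset and to any later use of DOAE, LNDOAE and DOAECFLCD as a censored duration.

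**What to change.** In the DOAE row of SAP 16.10.1:

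- For AONGO=Y, set DOAE = LSTCTDT − AESTDT + 1. The equivalent (LSTCTDT − TRTSDT + 1) − AESTDY + 1 uses only variables that the table already names.
- For AONGO=N, test the end-date imputation flag instead of AENDT: blank gives ADURN, D gives −99.
- For AONGO=N with a wholly missing end date, set DOAE to −99, in line with SAP 16.7.2.1.

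LNDOAE and DOAECFLCD need no change. The cost is three lines of dataset specification, with no new data and no change to any planned display. Made before programming, the change also avoids having to document a departure from the specification.
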